4.2. Treatment Assignment, Randomization, and Blinding

4.2.1. Randomization and Treatment Assignment

Randomization plan is reviewed and approved before the first subject enrollment and will be archived in eTMF after study database lock. The study site will manually execute the randomization and drug dispense according to Pharmacy Manual.

Sixteen subjects will be randomized in a 1:1 ratio to receive either BA (bempedoic acid 180 mg) (Cohort 1) or FCDP (Cohort 2). The IMP will be taken Day 1 through Day 6 of the treatment period. When the target number of subjects (8 in each cohort) is reached and all subjects have completed the 24-hour breast milk collection at the CRU, randomization will be closed. If a subject is randomized but did not complete the 24-hour breast milk collection in the CRU, she will be replaced with a new subject on the same treatment to ensure each cohort of the study has 8 evaluable subjects.

4.2.2. Blinding

This is an open-label study.

5. PLANNED ANALYSES

The following analyses will be performed for this study: Final Analysis

5.1. Interim Analyses

There will be no interim analyses in this study.

5.2. Final Analyses

All PK and safety analyses specified in this SAP will be performed by a CRO.

Additional ad-hoc analyses may be performed as needed.

6. ANALYSIS SETS

Inclusion of subjects in each analysis set will be finalized prior to the database lock of the study. Additional subsets may be explored as needed.

6.1. Full Analysis Set

Full Analysis Set (FAS, same as Safety Population in protocol) will consist of all randomized subjects who receive at least 1 dose of study drug – either BA (Cohort 1) or FCDP (Cohort 2). FAS will be used for summary of disposition, demographics and baseline characteristics, treatment exposure, study drug accountability, postpartum history, infant feeding practice, concomitant medications, and all safety data (including adverse events, clinical laboratory tests, physical examination, vital signs). The summaries will be conducted by cohort.

6.2. PK Analysis Set

The PK Analysis Set (PKS, same as PK population in protocol) will include all subjects in FAS who have at least 1 evaluable post-dosing milk ETC-1002 concentration data point. Data points affected by protocol deviation may be excluded from PK analyses but will remain in the PK concentration data listing.

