#### 14.3.2 Pharmacokinetic Population

The PK Population will include all subjects who complete the 24-hour breast milk collection after IMP administration on Day 6.

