1. INTRODUCTION

This statistical analysis plan (SAP) describes the rules and conventions to be used in the presentation and analysis of infant exposure, milk and plasma pharmacokinetic and safety data from healthy lactating women for Protocol 1002FDC-075, entitled *An Open-Label Postmarketing Milk-Only Lactation Study to Evaluate the Concentration of Bempedoic Acid and Bempedoic Acid and Ezetimibe in the Breast Milk of Healthy Lactating Women Administered Therapeutic Doses of Bempedoic Acid or Bempedoic Acid/Ezetimibe Fixed Combination Drug Product (FCDP)*, Amendment 1 (June 6th, 2023). The SAP will supersede the protocol in the event of any differences between the 2 documents in the plans for data analysis.

Analyses will be conducted using SAS® version 9.4 or higher and Phoenix WinNonlin version 8.4.

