8. STATISTICAL CONSIDERATIONS

8.1. Sample Size

A minimum sample size of 16 (8 subjects who receive BA [Cohort 1] and 8 subjects who receive FCDP [Cohort 2]) evaluable subjects (who complete the 6-day treatment period and the 24-hour breast milk collection in the CRU) is planned for this study. Subjects who are treated but do not complete the 24-hour breast milk collection in the CRU will be replaced with a new subject on the same treatment to ensure 8 evaluable subjects in each cohort for the PK analyses. All treated subjects will be in the FAS.

The sample size was not based on empirical or hypothesis testing criteria. The sample size was based on clinical and regulatory considerations and precedence in previous ETC-1002 studies (████████). The sample size is considered sufficient to address the primary objectives of the study.

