8.4. Missing Data Handling

Unless otherwise specified, missing data will not be imputed.

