17.3. PK Analysis for Primary Endpoints

The 1st primary endpoint - **daily infant dosage** (mg/day) of BA or EZE will be calculated as the amount of drug in breast milk collected over 24 hours (starting on Day 6 post study treatment) for individual subjects, where the amount of drug in breast milk is calculated as the sum of total drug concentration in each milk collection multiplied by the expressed milk volume in each milk collection.

Daily infant dosage (Dose_{ij}) = $\Sigma (C_{ij} \times V_{ij})$, where

Dose_{ij} = daily infant dose based on collected drug concentration in breast milk and expressed breast milk volume

C_{ij} = drug concentration in breast milk from each collection

V_{ij} = breast milk volume collected at each nominal timepoint

i = nominal timepoints within 24 hours post study treatment on Day 6

j = subjects (8 in each cohort, 16 in total)

- The 2nd primary endpoint - **relative infant dose (RID)** of BA (for Cohort 1 and 2 respectively) or EZE (for Cohort 2 only) equals the percent of the weight-adjusted maternal dosage consumed by infant via breast milk over 24 hours.

RID (%) = Estimated daily infant dosage (mg/day/kg) / Maternal dosage (mg/day/kg) x 100.

The estimated daily infant dosage will be calculated as the average drug concentration in breast milk over 24 hours after the Day 6 dose administration (C_{avg}) multiplied by 150 mL/day/kg, the estimated standard infant milk intake over 24 hours. Maternal dosage will be calculated as the mean maternal dosage (mg/day per kg baseline body weight determined on Day 1).

Estimated daily infant dosage (mg/day/kg) = C_{avg} (mg/ml) x 150 (ml/day/kg)

Maternal dosage (mg/day/kg) = daily dose of study treatment (mg/day) / baseline body weight (kg)

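### SAP 6.2 equates the PK Analysis Set with the protocol's 24-hour completers but admits anyone with one milk value, and no stated rule keeps a truncated sum out of daily infant dosage

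*SAP*

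**What the plan says.** Protocol 14.3.2: "The PK Population will include all subjects who complete the 24-hour breast milk collection after IMP administration on Day 6".

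SAP 6.2 presents its own set as identical to that one: "PKS, same as PK population in protocol) will include all subjects in FAS who have at least 1 evaluable post-dosing milk" ETC-1002 concentration. SAP 1 settles conflicts over data analysis: "The SAP will supersede the protocol in the event of any differences between the 2 documents".

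SAP 8.1 (Sample Size) treats an evaluable subject as one who finishes the six treatment days and the 24-hour collection. A treated non-completer is "replaced with a new subject on the same treatment to ensure 8 evaluable subjects in each cohort for the PK analyses", and "All treated subjects will be in the FAS".

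SAP 17.3 defines daily infant dosage as "the amount of drug in breast milk collected over 24 hours", computed as the sum of concentration times volume over the collections, with the index "j = subjects (8 in each cohort, 16 in total". RID uses Cavg, which is AUC24h divided by 24 h.

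On incomplete data, SAP 8.4 says "Unless otherwise specified, missing data will not be imputed". SAP 17.4 sets AUC24h and Cavg to not evaluable (NE) when fewer than three values lie above the LLOQ. SAP 8.4.2 and 17.4 set the Day 6 time-zero milk concentration equal to the 24-h trough.

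**The concern.** The two definitions describe different sets, although the SAP says they are one. A woman who pumps at 3 h and then stops is outside the protocol population. She is inside the SAP set, beside her replacement, so a cohort could hold more than the eight subjects in the dosage formula.

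This matters most for daily infant dosage, the first primary endpoint. It is a plain sum, so an uncollected interval simply contributes nothing. A partial total has the same units as a full one and would read as low infant exposure, which is the wrong direction for a lactation study to err in. With about eight women per cohort, one such value is visible in the mean and would probably set the minimum.

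**Working it through.** **1. The plan's own figures.** The planned number is 8 + 8 = 16. The SAP says it does not rest on hypothesis-testing criteria, so there is no formula to reproduce. The intervals in SAP 17.1 cover 3 + 3 + 3 + 3 + 4 + 4 + 4 = 24 h in seven collections.

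**2. Who can enter.** The first post-dose milk sample is taken 3 h after the Day 6 dose, so a woman who leaves before Day 6 cannot qualify. The route is a stop after the 3, 6, 9, 12, 16 or 20 h pump, which gives six possible stops.

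**3. Which rule would stop a partial sum.**
- SAP 8.4 bars imputation, so the gap is not filled.
- The three-value rule names only AUC24h and Cavg.
- SAP 6.2 allows data points affected by a deviation to be excluded. That is optional, and removing a point shortens the sum further.
- SAP 6 fixes set membership before lock and SAP 10 provides for deviation review. Neither states a completeness criterion.

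**4. Which set applies.** SAP 17.4 places descriptive analyses of PK concentrations and parameters on the PK Analysis Set. It then lists daily infant dosage and RID for summary by cohort without naming a set. Applying the PK Analysis Set to them is therefore an inference, though the natural one.

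**5. Size for daily infant dosage.** Assumptions, not in the documents: excretion is uniform over 24 h; eight completers each have true value 1; one partial collector has true value r.
- Fraction captured: f = t/24.
- Error in her own total: f − 1.
- Cohort mean against completers only: (r·f − 1)/9, with break-even at r = 1/f.
- Cohort mean against the mean had her full 24 h been collected: −(1 − f)·r/(8 + r).

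| Last pump | Values | f | Her own total | Mean vs completers, r = 1 | r = 2 | Break-even r | Mean vs her full collection, r = 2 |
|---|---|---|---|---|---|---|---|
| 3 h | 1 | 0.125 | −87.5% | −9.7% | −8.3% | 8.0 | −17.5% |
| 6 h | 2 | 0.250 | −75.0% | −8.3% | −5.6% | 4.0 | −15.0% |
| 9 h | 3 | 0.375 | −62.5% | −6.9% | −2.8% | 2.7 | −12.5% |
| 12 h | 4 | 0.500 | −50.0% | −5.6% | 0.0% | 2.0 | −10.0% |
| 16 h | 5 | 0.667 | −33.3% | −3.7% | +3.7% | 1.5 | −6.7% |
| 20 h | 6 | 0.833 | −16.7% | −1.9% | +7.4% | 1.2 | −3.3% |

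For r = 1 the last column would equal the r = 1 column. If a geometric mean is reported, r = 1 gives 0.125^(1/9) = 0.794 (−20.6%) for a stop at 3 h and 0.833^(1/9) = 0.980 (−2.0%) for a stop at 20 h.

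As a check on the uniform assumption, suppose instead that excretion declines from dosing with the 24 h half-life of Protocol 4.3. The first interval then holds 16.6% of the total and the last about 12%. Her own error becomes −83.4% for a stop at 3 h and about −12% for a stop at 20 h.

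**6. RID.** If all her values exceed the LLOQ, the three-value rule catches stops after 3 h and 6 h (one and two values). It does not catch the other four stops (three to six values). In those four the 24-h trough is missing, so the prescribed time-zero value does not exist. AUC24h, Cavg and RID then cannot be computed as written, and the SAP does not say what happens.

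**The case against.** The case on the other side is substantial.

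- **Intent.** The dosage is defined as a 24-hour amount, the formula indexes eight per cohort, and SAP 8.1 plans eight completers. A 9-hour sum does not meet that definition. A reader might infer that the SAP means to report partial sums; the documents do not support that. What is missing is a rule that enforces the evident intent.
- **Precedence.** Calling the sets the same could be read as adopting the protocol definition, so that no difference arises for the SAP to override. The operative criterion that follows is still the looser one, so the sentence cannot be right as it stands.
- **Link to the endpoint.** SAP 17.4 names no set for daily infant dosage. That is true, and the silence itself needs correcting.
- **RID.** A reader might infer that both primary endpoints are exposed in the same way. They are not: RID is largely protected, because AUC24h cannot be formed as prescribed without the 24-h sample.
- **Completeness.** Requiring a separate result from all seven pumps would go beyond Protocol 14.3.2. Both breasts are emptied each time, so milk from a skipped pump may be recovered at the next one with the cumulative amount largely intact. This stands, and it limits the fix.
- **Likelihood.** Collection is supervised and residential, non-completers are replaced, the listings show every profile, and the analysis is descriptive. All true. The documents give no expected number of partial collectors, and it may be zero.

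**Conclusion.** The SAP's statement that the two populations are the same is wrong as written. On the natural reading, no stated rule keeps a truncated sum out of daily infant dosage. For the woman concerned the error is always downward: 16.7% to 87.5% under uniform excretion.

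A reader might go further and conclude that the cohort mean must be biased low. That holds against the mean with her full collection, or if all women excrete equally. Against a completers-only summary the change ranges from −9.7% to +7.4% across the cases shown (r = 1 and r = 2). All cohort figures assume one partial collector added to eight completers.

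This should be fixed before the data are seen, but it is a conditional risk and not a demonstrated bias. For RID the defect is an unstated outcome after a stop at 9 h or later.

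**What to change.** Change the SAP wording; no new data are needed.

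1. In 6.2, define the set for the primary endpoints as in Protocol 14.3.2 (24-hour completers). Name that set for daily infant dosage and RID in 17.3 and in the summary list of 17.4.
2. Set daily infant dosage to NE for an analyte when milk from any part of 0-24 h was not collected, or when its volume or concentration is unavailable. A skipped pump whose milk was captured at the next emptying should not by itself make the total NE.
3. State the value a BLQ interval takes in the sum. SAP 8.4.2 excludes BLQ values that precede the last quantifiable one, which would remove a term.
4. Set AUC24h, Cavg and RID to NE without the 24-h sample.
5. Report n for each endpoint and analyte, and keep partial profiles in the listings.
6. Reconcile SAP 17.4, which places milk concentration summaries on both the PK Analysis Set and the FAS.

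The cost is that n may fall below eight in a cohort if a completer's sample is lost, since replacement depends on completing the collection.

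Separately, the missed-dose passages (Protocol 6.7 and 14.3.2.1 against 8.1, 9.4 and 10.3) need to be reconciled. This point does not depend on them.

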#### **4.3 Dose Selection**

A dose of bempedoic acid 180 mg once per day was selected based on approved doses by the US FDA ([Nexletol](#)) and the European Medicines Agency ([Nilemdo](#)). The dose for bempedoic acid/ezetimibe FCDP (bempedoic acid 180 mg/ezetimibe 10 mg) was selected based on approved doses by the US FDA ([Nexlizet](#)) and the European Medicines Agency ([Nustendi](#)). For additional information please refer to the most recent [IB](#), the [USPIs](#) for [Nexletol](#) and [Nexlizet](#) and the [SmPCs](#) for [Nilemdo](#) and [Nustendi](#).

Subjects enrolled in the study will be dosed for 6 consecutive days in order to reach steady-state concentrations of bempedoic acid or bempedoic acid and ezetimibe in plasma. Steady-state concentrations in plasma are expected after 5 to 7 days of repeat dosing as estimates of elimination half-life of bempedoic acid and ezetimibe are each approximately 24 hours. A once daily dosing regimen for 6 days will achieve plasma concentrations that are approximately 98% of steady-state levels. Six days of repeat dosing have been selected to ensure subjects are at steady-state plasma concentrations of bempedoic acid or bempedoic acid and ezetimibe for pharmacokinetic (PK) assessments.

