### **6.7      Subject Withdrawal and Replacement**

A subject is free to withdraw from the study at any time. Approximately 16 (8 bempedoic acid [Cohort 1] and 8 bempedoic acid/ezetimibe FCDP [Cohort 2]) healthy lactating female subjects will be enrolled. If a subject discontinues the study early or does not receive 6 daily doses of IMP or does not complete the 24-hour breast milk collection after Day 6 dosing, a replacement subject will be enrolled and assigned to the same treatment. The site must notify the Sponsor of any early withdrawals.

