### 9.4 Investigational Medicinal Product Adherence

On Day 2 through Day 5 subjects will document day and time IMP is taken in the Study Drug Diary and the diary will be submitted to study staff at check-in to the CRU on the evening of Day 5 (Visit T2). In addition, study staff will phone subjects on Day 2 through Day 5 to ensure subjects are taking IMP appropriately. Study staff will assess subject adherence through phone calls, review of the Study Drug Diary, and by counting the number of tablets returned at check-in to the CRU on the evening of Day 5. If a subject has missed a dose of IMP, the Sponsor will be notified immediately to determine if the subject should continue in the study or be replaced.

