#### 14.3.2.1 Primary Analyses

- Daily infant dosage and RID of bempedoic acid will be summarized for Cohort 1 subjects who receive once daily bempedoic acid for 6 consecutive days.
- Daily infant dosage and RID of bempedoic acid and ezetimibe will be summarized for Cohort 2 subjects who received once daily bempedoic acid/ezetimibe FCDP for 6 consecutive days.
- RID will be calculated as the ratio of total infant dose per kg body weight and maternal dose per kg body weight, multiplied by 100.

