17.4. PK Analysis for Secondary Endpoints

The secondary endpoints of this study are the following, which are based on PK assessments (see [Table 2](#)) for BA (ETC-1002), EZE, and their metabolite (ESP15228, ETC-1002-glucuronide, and EZE-glucuronide) of milk and plasma PK samples.

- Amount excreted in breast milk during each collection period, calculated as the product of analyte concentration and volume of milk collected per collection period.
- Area under the breast milk concentration-time curve (AUC_{24h}) over the 24-hour collection interval. To calculate AUC_{24h} , the initial milk concentration at time equal 0 hours on Day 6 will be set equal to the value of C_{trough} for each individual subject.
- Average drug concentration in breast milk (C_{avg}) calculated as $AUC_{24h}/24h$
- Peak milk concentration (C_{max})
- Time of peak milk concentrations (T_{max})
- Trough milk concentrations at 24 hours after the last dose on Day 6 (C_{trough})
- Plasma trough concentrations at 24 hours after the last dose on Day 6 (C_{trough})

Actual sampling times will be used in the final analyses of individual PK parameters. Predose sampling times will be set to zero. AUC_{24h} will be estimated by noncompartmental analysis (linear up/log down trapezoidal method) and estimates of C_{max} and t_{max} will be reported from observed values. If C_{max} occurs at more than one time point, t_{max} will be assigned to the first occurrence of C_{max} .

C_{avg} in milk will be calculated based on area under the milk concentration-time curve (AUC_{24h}) over the 24-hour collection interval.

$$C_{avg} (\text{mg/mL}) = AUC_{24h} (\text{mg} \cdot \text{h/mL}) / 24h.$$

If a subject had fewer than 3 data points above LLOQ, AUC_{24h} and C_{avg} will be set to “NE” (Not Evaluable).

M/P ratio is defined as the ratio of milk trough concentration and plasma trough concentration.

$$\text{M/P ratio} = C_{trough} (\text{Milk}) / C_{trough} (\text{Plasma})$$

All the descriptive analyses on PK concentration and PK parameters will be performed upon the PKS.

Collected milk volume, milk concentration of BA and its metabolites will be summarized by nominal sampling timepoints, and by cohort on FAS. Milk concentration of EZE and its metabolite will be summarized by nominal sampling timepoints for Cohort 2 only.

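### The SAP's PK Analysis Set has no dosing condition, so a woman who missed home doses but was kept in the study need not be removed from daily infant dosage and RID

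*SAP*

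**What the plan says.** The primary objective in SAP 2.1 is daily infant dosage and RID after six consecutive days of dosing. Protocol 14.3.2.1 describes the Cohort 1 primary summary as covering "subjects who receive once daily bempedoic acid for 6 consecutive days", with parallel wording for Cohort 2.

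The SAP's analysis sets do not carry that condition:

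- SAP 6.1: the FAS is "all randomized subjects who receive at least 1 dose of study drug".
- SAP 6.2: the PKS "will include all subjects in FAS who have at least 1 evaluable post-dosing milk ETC-1002 concentration data point".
- SAP 17.4: "All the descriptive analyses on PK concentration and PK parameters will be performed upon the PKS". SAP 17.3, which defines the two primary endpoints, names no analysis set of its own.
- SAP 6.2 also has a discretionary clause: "Data points affected by protocol deviation may be excluded from PK analyses but will remain in the PK concentration data listing".

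On missed doses, protocol 6.7 calls for a replacement when a woman "does not receive 6 daily doses of IMP". Protocol 9.4 instead leaves it to a case decision: "the Sponsor will be notified immediately to determine if the subject should continue in the study or be replaced". Protocol 8.1 does the same. SAP 4.2.1 and 8.1 tie replacement only to an incomplete milk collection.

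SAP 1 states that the SAP prevails over the protocol where their analysis plans differ.

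**The concern.** Doses on Days 1 and 6 are given by staff; those on Days 2 to 5 are taken at home. Suppose a woman misses one or more home doses, the sponsor lets her continue, and she then takes Day 6 and gives all seven milk collections. She meets every stated condition of the PKS.

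Nothing else in the SAP removes her. SAP 7.1 counts her as a treatment completer because she reaches the Day 6 visit. SAP 16 would class her as non-compliant, but that classification is reported on the FAS and is not linked to the PKS. The denominator of her RID in SAP 17.3 is still the full daily dose over baseline weight.

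Her milk would be below the steady state that six days of dosing is meant to reach. Including her lowers the reported infant exposure, which is the unfavourable direction for a study meant to inform breastfeeding decisions.

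**Working it through.** **Inputs.** Elimination half-life is about 24 h for both drugs (protocol 4.3). Dosing is once daily for six days. Milk is collected at 3, 6, 9, 12, 16, 20 and 24 h after the Day 6 dose. AUC24h is by linear-up/log-down, with the time-0 value set to the 24 h trough (SAP 8.4.2 and 17.4). Cavg = AUC24h/24, and RID is proportional to Cavg (SAP 17.3). Assumed, because the documents do not give them: linear kinetics, milk concentration proportional to plasma, and absorption ranging from instantaneous down to a first-order rate (ka) of 0.2 per h.

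**Step 1: the plan's own figure.** Protocol 4.3 states: "A once daily dosing regimen for 6 days will achieve plasma concentrations that are approximately 98% of steady-state levels". With a 24 h half-life, the fraction of steady state after n doses is 1 − 0.5^n. For n = 6 this is 1 − 0.015625 = 0.984, so the figure reproduces.

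**Step 2: one woman's loss, instantaneous absorption.** Exposure over the Day 6 interval is proportional to the sum of 0.5^(6−d) over the doses d taken. The full course gives 1 + 0.5 + 0.25 + 0.125 + 0.0625 + 0.03125 = 1.96875. For example:

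- Day 5 missed: (1.96875 − 0.5)/1.96875 = 0.746, a loss of 25.4%.
- Days 2 to 5 all missed: (1 + 0.03125)/1.96875 = 0.524, a loss of 47.6%.

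**Step 3: slower absorption, using the SAP's AUC24h.** At ka 0.2 per h with Day 5 missed, the loss is 29.6% in true AUC but 28.5% in the SAP's AUC24h. The imputed time-0 value offsets part of the loss, because her true pre-dose level is only about 0.65 of the value imputed. RID takes the SAP figure. Daily infant dosage does not use the imputed value; if milk output is steady, its loss follows true AUC (25.4% to 29.6%).

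**Step 4: effect on the cohort.** If her full-course exposure would equal the cohort mean, one such woman in 8 shifts the arithmetic mean by loss/8.

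| Home dose(s) missed | Loss in her AUC24h, Cavg and RID | Shift in arithmetic mean, 1 of 8 |
|---|---|---|
| Day 2 | 3.2% to 3.6% | 0.40% to 0.45% |
| Day 3 | 6.3% to 7.1% | 0.8% to 0.9% |
| Day 4 | 12.7% to 14.3% | 1.6% to 1.8% |
| Day 5 | 25.4% to 28.5% | 3.2% to 3.6% |
| Days 2 to 5 | 47.6% to 53.5% | 6.0% to 6.7% |

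For the geometric mean with Day 5 missed: 1 − 0.746^(1/8) = 3.6% and 1 − 0.715^(1/8) = 4.1%. The minimum and the spread can move more: if hers is the lowest value, the reported minimum carries her whole loss.

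**The case against.** Several points on the other side stand.

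- The protocol's own PK Population (14.3.2) has no dose count either, and the wording in 14.3.2.1 can be read as describing each cohort's regimen. Restriction is the more natural reading, since it matches the objective, but it is not the only one. SAP 8.1 also describes evaluable women as completing the six-day treatment period, although it uses this for sample size and not as a PKS condition.
- Daily calls, the diary and the tablet count should bring a missed dose to light before the collection starts. Missing all four home doses and still being kept is therefore unlikely.
- Non-compliance and deviations are reported, so a missed dose would not be hidden. But a reader could not tell from the RID table how much it had changed the result.
- The shift in the cohort mean is modest, and the study is descriptive.

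Two stronger readings are tempting, and the documents do not support them. A reader might infer that a woman replaced for missed doses is routinely averaged together with her replacement. Protocol 9.4 presents continuing and being replaced as alternatives. Under protocol 10.4.2 and 10.4.3, a woman who stops treatment or leaves the study early gives no 24-hour milk collection, so she would ordinarily have no milk value to qualify her. A ninth woman also does not fit the index of 8 per cohort in SAP 17.3. A reader might also infer that exclusions can be chosen once concentrations are known. The documents do not say when concentrations become available, and SAP 6 and 10 settle set membership and the deviation list before database lock. What remains is that the exclusion is optional and has no missed-dose criterion.

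**Conclusion.** The concern holds for a woman with a missed home dose who is kept in the study and completes the Day 6 collection: the SAP does not require her removal from the primary summaries. Her own RID would be understated by about 3% (Day 2 missed) to just over a quarter (Day 5 missed), and the cohort mean by at most a few percent for one such woman. The size rests on the protocol's 24 h half-life and the kinetic assumptions above. The direction, towards lower infant exposure, requires only that earlier doses still contribute on Day 6. The number of women affected is unknown and may be zero. The SAP should settle the rule because the primary objective is defined by six consecutive doses.

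**What to change.** In SAP 6.2 and 17.3, base the primary summaries of daily infant dosage and RID on PKS women with all six doses documented: staff records for Days 1 and 6, diary and tablet count for Days 2 to 5. List the remaining PKS women with the day or days missed, and show the all-PKS summary as a labelled sensitivity analysis. State that any replaced woman who nonetheless has Day 6 milk data is not in the primary summary. Reconcile the replacement triggers in protocol 6.7, 8.1 and 9.4 with those in SAP 4.2.1 and 8.1.

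The cost is SAP wording and one extra table, using data already collected. The downside is that a cohort's primary table could hold fewer than 8 women if one with a missed dose is kept and not replaced.
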